#### *Consent mechanism*

To avoid exposure of the research team, we will perform verbal consent of study subjects. Potentially interested participants will receive an electronic version (in PDF format) of the combined ICF/HIPAA authorization form via email or other method of their choice. After they have had an opportunity to read it, we will finalize the consent process over the phone, including an opportunity to clear any doubts/questions about the protocol. At that point, if patients decide to participate, we will invite a witness to record the verbal consent. The study team will document the consent process in writing. Participants will also fill a brief RedCap survey (using their unique 4-digit ID provided by the team) further documenting their consent. An example is shown below. Alternatively, patients may print the consent form at home, sign it and send us a digital photograph

of the last page. The latter mechanism will likely be used predominantly for outpatients. Consent by legally authorized patient representatives will be allowed.

 Survey response is read-only because it was completed via the e-Consent Framework.

 Survey options ▾

 **Response was completed on 08/08/2020 5:53pm.** Survey responses are not able to be edited once a participant has completed a survey. They are read-only.

Record ID **1001 (test patient)**

Record ID	1001 (test patient)
Please choose one of the following options:	  I have read the consent document and I wish to participate in the study   I have read the consent document and I DO NOT wish to participate in the study
I have had a chance to get all of my questions answered	  Yes   No
Today's date	 08-08-2020
Identifier provided by the study team	 100001

### **Version Control (Summary of Changes)**

## **V2 (August 15th, 2020):**

- Fixed typo, in which one component of the primary endpoint (FiO2/SpO2 ratio area under the curve) was incorrectly specified to be ranked from lowest to highest (the correct ranking is from highest to lowest).
- Fixed some typos throughout.
- Eliminated possible open label administration.
- Deleted mention of interim analysis at 75% enrollment (only one interim analysis, at 50% enrollment, is planned).
- Added mention of possibility of consent by the subject's authorized representative.
- Corrected time points in Figure 2 according to protocol text.
- Added sensitivity analysis with normalization for effect of atmospheric pressure on FiO2 above sea level.
- In order to have a universal main protocol while facilitating regulatory review/approval for countries outside the US, we have:
  - o Eliminated specific mention to the preparation that will be used in the main protocol, and have placed it in Appendix 3 (Fenofibrate prescribing information).
  - o We have also specified the consent process specific to the US in Appendix 3.
  - o Other country-specific regulatory requirements (particularly for countries outside the US) will be specified in appendix 3 as needed, when IRB and other regulatory submissions are prepared within a specific country.

## **V3 (November 10th, 2020)**

- Added exclusion criteria of intubated patients.
- Added possibility of participation for patients on pravastatin or rosuvastatin.
- Added that patients discharged within 24 hours of enrollment will be ranked as outpatients.
- Update of National Leaders (addition of new countries)
- Replaced [name] with [name] in DSMB (due to the fact that [name] declared a COI).

## **V4 (January 10th, 2021)**

- Eliminated possibility of single blinding administration, since with new grant support, full blinding (patient, investigator and adjudicator for symptom questionnaire) can be successfully implemented and mandated at all sites. Of note, no patient has been enrolled in single-label administration. Therefore, the entire trial will be double-blinded.
- Added fenofibric acid as a dose-equivalent preparation (which will be used in Colombia).
- Changed the number of participants enrolled to 700 and added power calculations for primary and secondary outcomes.
- Specified the exclusion of uncontrolled hypothyroidism, allowing enrollment of patients receiving a stable dose of thyroid replacement therapy for at least 6 weeks, with a documented normal TSH (primary hyperthyroidism) or free thyroxine (secondary or tertiary hypothyroidism) level at least 6 weeks after the last dose change. This is because concerns of thyroid myopathy (due to genetic/metabolic effects of thyroid deficiency on skeletal muscle) do not apply to patients who are on adequate thyroid replacement therapy.

## **V5 (November 2021)**

- Included the possibility of enrolling patients from outside of PennMedicine who reach out to us as a result of advertisements. In these instances, it may be necessary to perform laboratory testing through the Center for Human Phenomics Sciences.

### FEnofibRate as a Metabolic INtervention for Coronavirus Disease 2019 (COVID-19): A randomized controlled trial (FERMIN trial)

April 6, 2022

This document details the statistical analysis plan in detail, including analyses that were pre-specified prior to data locking and unblinding. The document follows the original protocol analysis plan, but includes more methodologic detail and additional pre-specified analyses that are based on data not available at the time the protocol was written. These include: (1) A stratified analysis according to the specific fenofibrate/fenofibric acid preparation used, given recent data suggesting that there may be differential potency of fenofibrate as opposed to fenofibric acid *in vitro*, at least in some viral strains and/or culture systems; (2) Stratified analysis suggested by the trial DSMB during the course of the study, such as according to country, baseline disease severity, and COVID-19 pandemic epochs in which specific strains predominated.

## ENDPOINTS

### Primary Endpoint

The primary endpoint is a composite global rank score that ranks patient outcomes according to the most severe outcome for each patient based on 5 factors: (1) time to death (ranked from shortest to longest, up to 30 days post-randomization), (2) the number of days supported by mechanical ventilation (invasive or non-invasive) or extracorporeal membrane oxygenation (until hospital discharge, up to 30 days post-randomization, ranked from longest to shortest); (3) The inspired concentration of oxygen/percent oxygen saturation (FiO2/SpO2) ratio area under the curve (until hospital discharge, up to 30 days post-randomization, ranked from highest to lowest); (4) For participants enrolled as outpatients who are subsequently hospitalized, the number of days out of the hospital during the 30 day-period following randomization (ranked from lowest to highest); (5) For participants enrolled as outpatients who don't get hospitalized during the 30-day observation period, the modified Borg dyspnea scale (mean value of assessments at ~5, and ~10 and ~15 days).

### Secondary Endpoints (Pre-specified in the protocol)

Secondary endpoints pre-specified in the protocol are:

- (1) Number of days alive, out of the intensive care unit, free of mechanical ventilation (invasive and non-invasive), extracorporeal membrane oxygenation (ECMO) or maximal available respiratory support in the 30 days following randomization.
- (2) A seven-category ordinal scale consisting of the following categories: 1, not hospitalized with resumption of normal activities; 2, not hospitalized, but unable to resume normal activities; 3, hospitalized, not requiring supplemental oxygen; 4, hospitalized, requiring supplemental oxygen; 5, hospitalized, requiring nasal high-flow oxygen therapy, noninvasive mechanical ventilation, or both; 6, hospitalized, requiring extracorporeal membrane oxygenation (ECMO), invasive mechanical ventilation, or both; and 7, death.
- (3) A global rank score similar to the primary endpoint, but using a more comprehensive COVID-19 symptom scale instead of the dyspnea Borg scale (Appendix 1 of Protocol).

**Exploratory endpoints** will include:

- (1) Time to all-cause death.
- (2) Time to hospitalization among subjects initially randomized as outpatients
- (3) Time to discharge among subjects initially randomized as inpatients
- (4) Number of days alive and out of the hospital during the 30 days following randomization.
- (5) A global rank score similar to the primary endpoint, but built only with factors 1-4

## ANALYSIS

**Intention to Treat Principle** Unless otherwise specified, all analyses are conducted on an 'as-randomized' basis, irrespective of adherence to treatment. This analysis follows the intention to treat principle pre-specified in the protocol.

### Descriptive Statistics (Intention to treat cohort)

Analyses will be for the overall cohort, stratified by arm and stratified by in/out patient status at randomization. The outcomes and baseline characteristics of the subjects will be described using proportions for categorical variables and means/medians as well as standard deviations (SD) and interquartile range (IQR) for continuous variables.

**Primary Analysis:** This analysis will use a two-sided van Elteren test, the stratified version of the Wilcoxon rank sum test. For each stratum, estimation, and 95% confidence intervals of differences between arms will use both the Hodges-Lehman median difference and the Mann-Whitney Parameter, the probability that a subject from the treatment arm has a score greater or equal to that of a subject for the control. In addition to the primary outcome, the Wilcoxon test will be used to test hypotheses involving the continuous secondary and exploratory outcomes.

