## 2.6. Randomization procedure

Following informed consent, participants will be randomized to one of the 2 treatment arms. A stratified blocked randomization with randomly permuted blocks will be performed based on site,

sex, age group, and inpatient vs. outpatient status, given the strong impact of these factors on outcomes in COVID-19. A sufficient number of complete blocks will be generated for each stratum so that randomized assignments are available for every eligible subject. Each block will contain an equal number of allocations to each arm.

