### 7.2. Data Analysis Plan

The sample, both the baseline characteristics and the outcomes, will be explored and described using graphical techniques and summary statistics (means, medians, proportions and measures of variability) as appropriate. The initial description will consider the sample as a whole as well as by treatment arm.

The primary outcome variable will be the global rank score, as used previously in several similar randomized controlled trials to facilitate evaluation of composite outcomes of binary and continuous findings accounting for censorship for death. The predictor of interest for all outcomes will be randomized intervention (fenofibrate vs. control), with analyses based upon the total number of randomized participants. Initial descriptive estimates of all measures will be generated for study participants by treatment group. Statistics will include estimates of central tendency, measures of variability, and derived moments of skewness and kurtosis. Analyses of distributional properties will be performed to determine if variance stabilizing or normalizing transformations should be applied. Outliers will be assessed via visual inspection of distributions and checked for accuracy. Additionally, the intervention groups will be compared using Fisher's Exact tests.

The primary and secondary outcomes will be analyzed using a two-sided Wilcoxon rank sum test. Estimation, and 95% confidence intervals, of the differences between arms will be based on the Hodges-Lehman median difference as well as the Mann-Whitney Parameter, the probability that a subject from the fenofibrate arm has a score greater or equal to that of a subject for the control. This will be followed by a more comprehensive linear regression analysis allowing for assessments of the treatment effect on each continuous outcome of interest while controlling for effects of covariates including age, sex, inpatient vs. outpatient status at enrollment,  $\text{FiO}_2/\text{SpO}_2$  at the time of enrollment, ethnicity, body mass index, altitude above sea level and history of diabetes at baseline.

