### Regression models

Linear regression analysis to estimate the treatment effect for each continuous outcome of interest will adjust for covariates including age, sex, inpatient vs. outpatient status at enrollment, FiO2/SpO2 at the time of enrollment, ethnicity, body mass index, altitude above sea level and history of diabetes at baseline. Although not specified in the initial protocol, at the recommendation of the DSMB, we will add Country as a fixed effect with the goal of adjusting for a broad indicator of treatment practices, timing of variants, and timing of surges. We will also perform sensitivity analyses clustered study site.

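### The SAP attaches effect estimates to the primary van Elteren test only within unnamed strata, and states no stratum-combined estimate to match the primary p-value

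*SAP*

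**What the plan says.** On the primary analysis the SAP states: "This analysis will use a two-sided van Elteren test, the stratified version of the Wilcoxon rank sum test". The next sentence deals with estimation: "For each stratum, estimation, and 95% confidence intervals of differences between arms will use both the Hodges-Lehman median difference and the Mann-Whitney Parameter". Neither sentence says what the strata are.

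The nearest candidate is the line that opens the same SAP section: "Analyses will be for the overall cohort, stratified by arm and stratified by in/out patient status at randomization". That line introduces descriptive summaries. Another candidate is the set of randomisation factors in protocol section 2.6, namely site together with "sex, age group, and inpatient vs. outpatient status".

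Protocol section 7.2 planned an unstratified two-sided Wilcoxon rank sum test, with this estimation rule: "Estimation, and 95% confidence intervals, of the differences between arms will be based on the Hodges-Lehman median difference as well as the Mann-Whitney Parameter". No stratum is mentioned there.

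The SAP introduction describes its relation to the protocol: "The document follows the original protocol analysis plan, but includes more methodologic detail and additional pre-specified analyses". Under Regression models it adds an analysis of all patients: "Linear regression analysis to estimate the treatment effect for each continuous outcome of interest will adjust for covariates". The covariates include inpatient or outpatient status, and Country is added as a fixed effect.

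**The concern.** A van Elteren test combines the strata into one statistic and one p-value. The effect size that belongs beside it is a combination of the stratum effects using the same weights. The SAP changed the test from unstratified to stratified and, in the next sentence, placed estimation inside the strata. As written, the primary result is one p-value with a set of stratum intervals, each based on part of the sample and each wider than an overall interval.

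Two things are at stake. First, the primary result has no stated effect size and interval on the scale of its own test. Second, the stratum intervals are the only estimates the SAP attaches to that test, so readers will lean on them. With a uniform effect, one interval will often exclude no effect while another does not, and that is easily mistaken for an effect confined to one stratum.

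**Working it through.** **Inputs.** From the protocol: 700 participants, 1:1 allocation (350 per arm), 80% power at a final alpha of 0.0492 (sections 2.5 and 7.1). Not in the documents, so assumed: two strata (inpatient and outpatient), a split from 50:50 to 90:10, equal arms within each stratum, and the same true Mann-Whitney parameter θ in each stratum.

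**The plan's own figure.** Section 7.1 derives 80% power for an 11% difference in median rank scores from 10,000 simulations. The simulated distributions are not given, so this figure can be neither confirmed nor refuted. I instead solve for the θ that gives 80% power.

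**Effect size implied by 80% power.** With n1 and n0 the arm sizes and N their sum,

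SE(θ) = √[(N+1)/(12·n1·n0)] = √[701/(12·350·350)] = 0.02184.

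The required standardised effect is 1.967 + 0.842 = 2.808, so θ = 0.5 + 2.808 × 0.02184 = 0.561. This is back-solved and is not a figure in the documents.

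**Interval width.** Half-width = 1.96 × SE(θ):

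| Sample | Half-width | 95% CI centred on 0.561 |
|---|---|---|
| 700 (overall) | 0.043 | 0.519 to 0.604 |
| 350 | 0.061 | 0.501 to 0.622 |
| 210 | 0.078 | 0.483 to 0.640 |
| 140 | 0.096 | 0.465 to 0.657 |

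**What the stratum intervals would show.** A stratum with share p of the sample has a z-statistic with mean 2.808·√p. At 50:50 both means are 1.99; at 80:20 they are 2.51 and 1.26. Two million simulated pairs per split, combined as √p·z1 + √(1−p)·z2, with the overall test at 0.0492 and stratum intervals at 95%, give the following chances that none, exactly one or both intervals exclude no effect in favour of treatment. The last column is the chance, given overall significance, that both point estimates favour treatment.

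| Split | None / one / both, all trials | None / one / both, given overall significance | Both estimates favour treatment, given significance |
|---|---|---|---|
| 50:50 | 24 / 50 / 26% | 10 / 57 / 33% | 99% |
| 60:40 | 24 / 51 / 25% | 10 / 59 / 31% | 99% |
| 70:30 | 23 / 55 / 22% | 9 / 64 / 27% | 97% |
| 80:20 | 22 / 61 / 17% | 7 / 71 / 21% | 93% |
| 90:10 | 21 / 69 / 11% | 5 / 82 / 13% | 85% |

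Simulating 20,000 trials per split with actual van Elteren statistics, for splits from 50:50 to 80:20, gave the same pattern (for example 57% and 72% exactly one, given significance, at 50:50 and 80:20).

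**Sensitivity.** At 90% overall power, exactly one interval excludes no effect in 47% of trials at 50:50 and 63% at 80:20 (49% and 67% given significance). At 80% power with four or eight equal strata, the figures are 42% and 37% (45% and 37% given significance).

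**The matching estimate.** The van Elteren statistic sums each stratum's rank-sum deviation divided by N+1. That deviation equals n1·n0·(θ − 0.5), with ties counted as one half. The test therefore weighs the stratum θ values by n1·n0/(N+1). At 80:20 the weights are 280·280/561 = 139.8 and 70·70/141 = 34.8, or 80% and 20%, and the combined half-width is 0.043, the same as for the whole sample.

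**The case against.** The strongest reply is that overall estimates do exist. The protocol's between-arm estimates are nowhere withdrawn, the SAP says it follows the protocol, and its regression gives a treatment effect in all patients adjusted for inpatient or outpatient status. An unadjusted mean-rank difference is also just a rescaled Mann-Whitney parameter: 0.0613 × 700 = 42.9 ranks. This stands as far as it goes, so it would be wrong to say that the plan has no overall estimate. It does not close the gap. The protocol's estimate goes with an unstratified test, and the regression ranks across strata and adjusts for several further covariates and Country, so neither need agree with the van Elteren result. The SAP line on the overall cohort promises proportions, means, medians and spread, not a treatment effect with an interval.

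A reader might also infer that a uniform effect will usually look confined to one stratum. The documents do not support that as a general statement. At 50:50 it is an even chance, it is not a majority with four or eight strata, and the strata are not named. Nor does the SAP ask anyone to judge efficacy by significance within strata. Its subgroup section treats inpatient or outpatient status as exploratory and hypothesis-generating, and protocol section 7.3 plans an assessment of effect modification. Wide stratum intervals do not contradict a significant pooled test, and under a uniform effect a 5% heterogeneity test would be falsely significant in only about 5% of trials.

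**Conclusion.** The point holds in this form: the SAP leaves the van Elteren strata unnamed, specifies estimates and intervals for that test only within strata, and states no stratum-combined estimate to match the primary p-value. It is a gap in reporting and interpretation, and a change to the primary estimation rule that the SAP does not explain.

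The percentages rest on two strata, a uniform effect and a θ back-solved from 80% power; the inpatient to outpatient split is unknown and was varied. They show how easily stratum intervals could be misread, not that they will be. The loss of precision from relying on a stratum interval depends only on sample size and holds whatever the effect.

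**What to change.** In the SAP's Primary Analysis paragraph:

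1. Name the strata used in the van Elteren test.
2. Make the effect estimate the weighted average of the stratum Mann-Whitney parameters, with weight n1·n0/(N+1) per stratum, and report it with its 95% CI beside the primary p-value.
3. Keep the stratum Hodges-Lehmann and Mann-Whitney estimates as secondary, with a test of heterogeneity between strata.

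The cost is a sentence or two in the SAP and a few lines of code. No new data are needed, and the test, alpha and sample size stay as they are.

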### 3. ENDPOINTS

The **primary endpoint** of the trial will be a global rank score that ranks patient outcomes according to 5 factors: (1) time to death (ranked from shortest to longest, up to 30 days post-randomization), (2) the number of days supported by mechanical ventilation (invasive or non-invasive) or extracorporeal membrane oxygenation (until hospital discharge, up to 30 days post-randomization, ranked from longest to shortest); (3) The inspired concentration of oxygen/percent oxygen saturation ( $\text{FiO}_2/\text{SpO}_2$ ) ratio area under the curve (until hospital discharge, up to 30 days post-randomization, ranked from highest to lowest); (4) For participants enrolled as outpatients who are subsequently hospitalized, the number of days out of the hospital during the 30 day-period following randomization (ranked from lowest to highest); (5) For participants enrolled as outpatients who don't get hospitalized during the 30-day observation period, the modified Borg dyspnea scale (mean value of assessments at ~5, ~10 and ~15 days). Patients who are enrolled as inpatients but discharged within 24 hours of receiving the first dose of the study medication will be ranked similarly to outpatients.

The global rank score has several advantages compared to binary outcomes (e.g., all-cause death) or time-to-event outcomes (e.g., time to death). It incorporates information about each of the highest-priority events in COVID-19, but allows these events to be prioritized within a single endpoint. For instance, the principal outcome of interest is death, but even if there is no difference in rate of death, we would still be interested in a shorter duration of invasive respiratory support, a shorter duration of hospital admission with better oxygenation parameters, and so on. This maximizes study power and minimizes the number of participants that need to be enrolled in order to detect clinically-meaningful differences.

**Figure 2** demonstrates how participants will be ranked hierarchically according to their clinical course. All primary analyses will be performed on an intent-to-treat basis.

**Secondary endpoints** will include:

- (1) Number of days alive, out of the intensive care unit, free of mechanical ventilation (invasive and non-invasive), extracorporeal membrane oxygenation (ECMO) or maximal available respiratory support in the 30 days following randomization.

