### Sensitivity Analyses

1. **Per-Protocol and As-Treated Analysis.** The extent of non-adherence to protocol will be described by arm. Cumulative event plots will be used to compare non-adherence to protocol (as a binary event) by arm. If there is a substantial difference in non-adherence

across treatment arms, we will adjust for non-adherence in the secondary analyses of the primary endpoint

2. The  $\text{FiO}_2/\text{SpO}_2$  ratio will be normalized for altitude above sea level (atmospheric pressure) using standard equations.
3. **Incomplete Data** While missing data is an inevitable problem in longitudinal studies, we will make every possible effort to ensure final assessments for all participants, including those opting to discontinue study participation. Possible mechanisms for missingness-missing completely at random (MCAR), missing at random (MAR), nonignorable or not missing at random (NMAR)-will be evaluated prior to implementing methodology intended to minimize bias from missing data. We anticipate that <5% of randomized subjects will have missing data in the components required to compute the study outcomes. Imputation is not commonly used for rank-based statistical methods such as the van Elteren or Wilcoxon Rank-sum test. If the missingness rate exceeds 5%, we will carry out a sensitivity analysis of the primary outcome using linear regression with multiple imputation. The primary analysis will be a complete case analysis.

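### The SAP does not name its van Elteren strata and appears to test the other global rank scores with an unstratified Wilcoxon test, which can cost much of their power when the inpatient/outpatient mix is fairly even

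*SAP*

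**What the plan says.** On the primary endpoint the SAP (Primary Analysis paragraph) states: "This analysis will use a two-sided van Elteren test, the stratified version of the Wilcoxon rank sum test". It promises estimates and confidence intervals within each stratum, but no section lists the strata. Inpatient/outpatient status appears just above, in the paragraph on descriptive statistics, where results are to be "stratified by arm and stratified by in/out patient status at randomization".

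For the other outcomes the same paragraph says, after a clause linking back to the primary outcome, that "the Wilcoxon test will be used to test hypotheses involving the continuous secondary and exploratory outcomes". The sentence covers continuous outcomes only. The seven-category scale therefore depends on protocol 7.2, which says: "The primary and secondary outcomes will be analyzed using a two-sided Wilcoxon rank sum test". No strata are mentioned there. In its note on incomplete data the SAP refers to "rank-based statistical methods such as the van Elteren or Wilcoxon Rank-sum test", as if to two different tests.

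Two design features bear on this. Protocol 2.6 randomises in permuted blocks by site and by "sex, age group, and inpatient vs. outpatient status, given the strong impact of these factors on outcomes in COVID-19". The rank score is also built partly on enrolment setting. Factor 4 begins "For participants enrolled as outpatients who are subsequently hospitalized, the number of days out of the hospital", and factor 5 is likewise confined to outpatients. Protocol section 3 adds that inpatients "discharged within 24 hours of receiving the first dose of the study medication will be ranked similarly to outpatients".

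**The concern.** Factors 4 and 5 rank above factors 1-3 and belong almost entirely to people enrolled as outpatients, so most outpatients rank better than most inpatients whatever treatment they receive. The separation is not complete. Deaths and ventilated patients from both groups mix at the bottom, and early-discharged inpatients join the outpatients.

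In a pooled Wilcoxon test, many treatment-control pairs therefore consist of one inpatient and one outpatient, and their order says little about the drug. The pooled null variance also includes the inpatient/outpatient difference, which stratified allocation has already balanced between arms. The test statistic is too small relative to its assumed standard error.

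Two things are at stake. The symptom-scale and factors 1-4 rank scores may have far less power than the design could give them. The primary test avoids this only if inpatient/outpatient status is among its unnamed strata. Site, sex, age group and country are other plausible choices, and each set gives a different p-value and different within-stratum estimates.

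**Working it through.** **Inputs from the documents.** N = 700, 1:1 allocation, two-sided test; final alpha 0.0492 and 80% power for an 11% difference in median rank scores (protocol 7.1); randomisation stratified by inpatient/outpatient status (protocol 2.6). The inpatient share and tier distributions are not given, so both are assumed below.

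**The plan's own figure.** Noether's formula for the Wilcoxon test is power = Φ(δ√(3N) − z), where δ is the Mann-Whitney probability minus 0.5. With √2100 = 45.83, z = 1.967 and 80% power, δ = (1.967 + 0.842)/45.83 = 0.0613. That is 0.0613 × 700 = 42.9 ranks, or 12.2% of the mean rank of 350.5. If 11% is read as a share of the mean rank, δ ≈ 0.0551 and power is 71%. Other readings give 43% to over 99%. Without the tier distributions, the stated 80% can be neither confirmed nor refuted.

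**Effect size used.** Under proportional odds, the Mann-Whitney probability is OR(OR − 1 − ln OR)/(OR − 1)². At OR 1.45 this is 1.45 × (0.45 − 0.3716)/0.2025 ≈ 0.562, so δ ≈ 0.062. This OR gives a stratified test about 80% power at N = 700.

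**Closed form, complete separation.** Let p be the inpatient share, with the same effect in both strata. Only within-stratum pairs carry treatment information, and they are p² + (1 − p)² of all pairs. Under stratified 1:1 allocation the pooled z has SD √(p³ + (1 − p)³) instead of 1. With van Elteren at 80% power (mean z = 1.967 + 0.842 = 2.81):

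- p = 0.5: mean 0.50 × 2.81 = 1.40, SD 0.50; power Φ((1.40 − 1.967)/0.50) = 13%
- p = 0.3 or 0.7: mean 0.58 × 2.81 = 1.63, SD 0.61; power 29%
- p = 0.2 or 0.8: mean 0.68 × 2.81 = 1.91, SD 0.72; power 47%
- p = 0.1 or 0.9: mean 0.82 × 2.81 = 2.30, SD 0.85; power 65%

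Type I error of the plain test is 2Φ(−1.967/SD): 0.008%, 0.12%, 0.64% and 2.1% in the same order.

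**Simulation with partial overlap, symptom-scale score (secondary 3).** 2,000 trials per cell at alpha 0.0492. Assumptions: inpatients 10-15% deaths and 10-15% ventilated; outpatients 1-3% each and 6-10% hospitalised; 30% of outpatients tied at the best value; within-stratum OR 1.45.

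| Inpatient share | Plain Wilcoxon | van Elteren |
|---|---|---|
| 50% | 18-26% | 79-82% |
| 30% or 70% | 30-41% | 79-82% |
| 20% or 80% | 46-53% | 79-82% |
| 10% or 90% | 65-68% | 79-82% |

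Plain type I error was 0.05-2.5%.

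**More overlap.** If hospitalised outpatients are ranked within factor 3 and 10% of inpatients are ranked as outpatients, plain power is 53-73% against 79-81%. If 25% are, it is 65-77%.

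**A different overlap model.** 1,500 trials per cell at alpha 0.05, for a Borg-type score. Assumptions: 10% of outpatients hospitalised, a third of them ranked among the worst inpatients; 5% of inpatients discharged early. Plain against van Elteren: 68% vs 77% at 10% inpatients, 47% vs 80% at 30%, 36% vs 80% at 50%, 45% vs 79% at 70%, and 70% vs 81% at 90%. Under the null at 50% inpatients, the plain test rejected in about 0.2% of trials and van Elteren in about 5%.

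**Factors 1-4 score (exploratory 5).** First simulation model, never-hospitalised outpatients tied at best:

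| Inpatient share | Plain Wilcoxon | van Elteren |
|---|---|---|
| 10-50% | 0.2-19% | 33-66% |
| 70% | 23-32% | 68-72% |
| 80-90% | 47-65% | 74-77% |

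**Outcomes not built on enrolment setting.** For a generic continuous outcome whose strata differ by OR 3 or OR 10, at 30-50% inpatients, plain power is 76-77% or 64-69% against 79-81%.

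**The case against.** The strongest counter-argument is textual. The opening clause of the SAP sentence ties the other outcomes to the primary, which is tested by van Elteren, so the Wilcoxon test named there may mean the stratified version. Inpatient/outpatient status is also the only patient characteristic named as a stratifier in that part of the SAP. This stands as a possible reading. It does not settle the matter, because the SAP says it follows the protocol analysis plan, protocol 7.2 has no strata, and the incomplete-data note treats the two tests as distinct. Either reading needs a sentence to confirm it.

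The second argument concerns size. OR 1.45 is chosen to give van Elteren about 80% power and is not the protocol's stated effect. At 50% inpatients it amounts to only about a 2.6% difference in median rank, or 6.7% in mean rank, relative to the overall mean rank. With OR 2.0 at that mix (mean-rank difference about 12%), the plain test has 92% power. That is correct, and it means the lowest figures apply to effects below the protocol's target on that scale. At 30% inpatients, however, the scenario does correspond to about 11%, and plain power is still only about 34%.

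Third, the planned regression adjusts for inpatient/outpatient status, and subgroup estimates by status are planned. Both help interpretation, but neither replaces the named hypothesis test. Finally, the affected scores are secondary and exploratory, and for the factors 1-4 score even the stratified test reaches only 33-66% when inpatients are 10-50%. Both points limit the importance of the issue without removing it.

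**Conclusion.** The concern holds. That the van Elteren strata are unnamed is plain from the text and needs no assumption. That the other rank scores are tested without strata is the natural reading, not a certain one.

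If the plain test is meant, it is conservative and loses power on the symptom-scale and factors 1-4 scores. For the symptom-scale score the loss ranges from a few points with heavy overlap, through about 10-15 points at a 10/90 or 90/10 mix, to more than 50 points at an even mix with limited overlap. These sizes rest on an assumed mix, assumed tier rates and overlap, and a similar effect in both strata. In every scenario reported the stratified test was the more powerful, and stratifying does not inflate false positives. The days-alive outcomes and the seven-category scale were not simulated; the generic case suggests a smaller gain there.

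**What to change.** In the SAP's Primary Analysis paragraph, name inpatient/outpatient status at randomisation as a van Elteren stratum. Other randomisation factors may be added where cells are large enough, and should be listed if used. State that the same stratified test applies to secondary rank score (3) and exploratory rank score (5), and also to the days-alive outcomes and the seven-category scale, which the SAP sentence on continuous outcomes does not cover. Align the test named in protocol 7.2.

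The cost is one SAP paragraph and one protocol sentence. The stratifying variable is already recorded at randomisation, so no additional patients or data are required.
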